#### **5.2.4. Vitiligo Quality of Life (VitiQoL)**

The Vitiligo Quality of Life (VitiQOL) will be completed according to the Schedule of Visits and Assessments ([Section 1.3](#)). The VitiQOL is an instrument designed to assess disease specific health-related quality of life (HRQL) in patients suffering from vitiligo and also provide an objective measure of disease status, burden of disease, and treatment outcome ([Appendix 2](#)). It consists of 16-item questionnaire with a 7-point numerical scale from 0 - Not at all to 6 - All of the time.

#### **5.2.5. Vitiligo Noticeability Scale (VNS)**

The Vitiligo Noticeability Scale (VNS) is a 5-point scale which compares vitiligo from before treatment to how noticeable the vitiligo is at the time the VNS is performed. The VNS will be completed by subjects with respect to vitiligo on the facial target patch. The target patch on the face is selected by the subjects as being the patch that they would most like to see an improvement in. The photos taken of the facial target patch at the Baseline visit prior treatment and at the subsequent visits will be used as reference for the assessment ([Appendix 3](#)).

#### **5.2.6. Facial Static Investigator Global Assessment (FsIGA)**

The Facial Static Investigator Global Assessment (FsIGA) is a global score of vitiligo severity for the face only. The outcome measure incorporates location, distribution, size, depigmentation within lesions and presence or absence of signs of activity. Examination of skin should be performed with both normal lighting and Woods lamp ([Appendix 4](#)).

#### **5.2.7. Patient Global Impression of Change-Vitiligo (PaGIC-V)**

The PaGIC-V is an assessment of improvement by the subject and is to be evaluated in this study **specifically with respect to facial vitiligo**. It is a 7-point scale comparing facial vitiligo at baseline with the subject's treated facial vitiligo at the study visit. ([Appendix 5](#))

## **5.3. Other Evaluations**

### **5.3.1. Medical Photography**

Digital Photography will be conducted at all sites for all subjects according to the Schedule of Visits and Assessment ([Section 1.3](#)). Photos will be taken of the facial target patch at the Baseline visit prior treatment and at the subsequent visits as reference for the VNS assessment. Fixed, multi-angle photos will be taken at select sites for additional evaluation.

### **5.3.2. Pharmacokinetics Assessment**

PK sampling will be performed according to the Schedule of Visits and Assessments ([Section 1.3](#)) for all subjects at all sites:

- PK will be evaluated through trough/pre-dose sampling at Baseline, Week 4, Week 12, and Week 24.

Subjects should apply investigational product 11-12 hours before the PK collection time.

PK samples will be collected while the subject is having safety labs drawn at applicable visits. The PK samples will be completed prior to investigational product application in the clinic. Ensure investigational product is not applied in the area where PK will be drawn.

## **5.4. Final Study Visit**

The final study visit will take place at approximately Week 25. The procedures performed during this visit are as described in the Schedule of Visits and Assessments ([Section 1.3](#)). A 7-day scheduling window is allowed for this visit. Adverse events will be recorded as reported by the subject and followed to resolution (as necessary).

## **5.5. Early Termination Visit**

If a subject is withdrawn or wishes to exit the study prior to the final study visit, an early termination visit will be scheduled. This visit should include the procedures and assessments that would be performed at the Week 24 visit as described in the Schedule of Visits and Assessments ([Section 1.3](#)).

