### 1.3. Schedule of Visits and Assessments

Study Procedure	Screen	Baseline Day 1	Wk 4 Day 29	Wk 8 Day 57	Wk 12 Day 85	Wk 16 Day 113	Wk 20 Day 141	Wk 24 Day 169	Wk 25 Day 176
Visit	1	2	3	4	5	6	7	8	9
Visit Window	-35 days		+/- 5 days	+/- 5 days	+/- 5 days	+/- 5 days	+/- 5 days	+/- 7 days	+/- 7 days
Informed consent	X								
Demographics	X								
Fitzpatrick skin type assessment	X								
Medical and surgical history	X								
Physical examination a	X	X			X				X
Vital signs, height, weight b	X	X	X	X	X	X	X	X	X
I/E criteria	X	X							
Randomization		X							
Hematology, Serum Chemistries, UA, TSH/T4	X	X	X		X			X	
Lipid (Fasting) c		X						X	
Resting 12-lead ECG	X		X		X			X	
BSA d (Full Body), T-VASI e	X	X			X			X	
F-BSA d , F/N-BSA d , BSA (Hands, Forearms, Elbows) d , F-VASI e , F/N-VASI e , FOREARM-VASI e , HAND-VASI e , FsIGA f	X	X	X	X	X	X	X	X	X
VNS g , PaGIC-V h			X	X	X	X	X	X	
VitiQoL i		X	X	X	X	X	X	X	
Local Tolerability Assessments j		X	X	X	X	X	X	X	
Digital Photography k		X	X	X	X	X	X	X	
Urine pregnancy test l		X	X	X	X	X	X	X	X
Serum pregnancy test m	X								
Follicle-Stimulating Hormone (FSH) n	X								

Study Procedure	Screen	Baseline Day 1	Wk 4 Day 29	Wk 8 Day 57	Wk 12 Day 85	Wk 16 Day 113	Wk 20 Day 141	Wk 24 Day 169	Wk 25 Day 176
PK Sampling o		X	X		X			X	
NB-UVB Phototherapy in clinic p		X							
Return of USB stick to site for phototherapy data uploading q			X	X	X	X	X	X	
Dispense IP kit r		X	X	X	X	X	X		
IP application in clinics s		X	X	X	X	X	X		
Dispense/review diary		X	X	X	X	X	X		
Weigh IP tubes t		X	X	X	X	X	X	X	
Compliance calculation u			X	X	X	X	X	X	
Adverse event assessment v	X	X	X	X	X	X	X	X	X
Concomitant medications	X	X	X	X	X	X	X	X	X

a Limited physical examination: skin, lungs, and heart only

b Height will be measured at Baseline only. Weight will be collected at screening, baseline and Week 24.

c Fasting required for a minimum of 8 hours prior to blood draw

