## 5. STUDY PROCEDURES

### 5.1. Safety Assessments

The Schedule of Visits and Assessments ([Section 1.3](#)) summarizes the clinical procedures to be performed at each visit. Individual clinical procedures are described in detail below. Additional evaluations/testing may be deemed necessary by the PI and/or the Sponsor for reasons related to subject safety.

This study assesses the safety, efficacy, and PK of ARQ-252 cream 0.3% and vehicle cream in combination with active or sham phototherapy. Safety will be determined by evaluating physical examinations, 12-lead ECGs, vital signs/weight, clinical laboratory parameters, local tolerability assessments, and AEs as outlined in the Schedule of Visits and Assessments ([Section 1.3](#)). Subjects will be monitored for the reactivation of herpes simplex virus or varicella zoster virus following the initiation of phototherapy treatment. In addition, subjects who will treat vitiligo on the hands will be monitored for changes in the nails following the initiation of phototherapy treatment. Changes noted from these assessments will be recorded in the CRF.

If deemed necessary, additional safety assessments will be performed at the discretion of the Investigator.

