### 5.1.3. Physical Examination

Physical examinations will be performed according to the Schedule of Visits and Assessments (Section 1.3). The physical exam will be limited to skin, lungs and heart only.

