#### **6.3.3. Medical History and Physical Examinations**

Clinically significant changes observed during physical examination will be captured as adverse events and included in AE tabulations.

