### 3. Overall Study Design and Plan

This is a 24-week, parallel group, double blind, vehicle-controlled study for the treatment of subjects with non-segmental facial vitiligo. This study was planned to include both male and female adults having a facial BSA  $\geq 0.25\%$  and F-VASI  $\geq 0.25$ . A total of 500 subjects were planned to be randomized. After having met all inclusion criteria, and none of the exclusion criteria, subjects were to be randomized in a 3:3:3:1 ratio as mentioned below in Section 3.4. Screening for up to 5 weeks followed by 24 weeks of treatment phase was planned for this study. In addition to the study drug ARQ-252 cream and vehicle cream, subjects were randomized to receive Daavlin series NB-UVB active or sham units. Subjects have to record the date and time each dose has been applied, any missed doses, and any additional comments. There was a follow-up visit approximately 1 week after treatment has been completed.

Upon the sponsor discretion, this study was terminated and none of the subjects could finish the entire treatment period. All the subjects that were currently enrolled have been early terminated and subjects that are in screening have been screen failed. Emergency unblinding was performed after following Premier Research SOPs.

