## 4. Statistical Analysis and Reporting

### 4.1. Introduction

Data processing, tabulation of descriptive statistics, calculation of inferential statistics, and graphical representations will primarily use SAS (release 9.4 or higher). If the use of other software is warranted, the final statistical methodology report will detail what software was used for what purposes.

Continuous (quantitative) variable summaries will include the number of subjects (n) with non-missing values, mean, standard deviation (SD), median, Q1, Q3, minimum, and maximum.

Categorical (qualitative) variable summaries will include the frequency and percentage of subjects who are in the particular category or each possible value. In general, the denominator for the percentage calculation will be based upon the total number of subjects in the study population for the treatment group, unless otherwise specified. The denominator for by-visit displays will be the number of subjects in the relevant study population with non-missing data at each visit.

The minimum and maximum will be reported with the same degree of precision (i.e., the same number of decimal places) as the observed data. Measures of location (mean, median, Q1, and Q3) will be reported to 1 degree of precision more than the observed data and measures of spread (SD) will be reported to 2 degrees of precision more than the observed data.

Percentages will be presented to 1 decimal place, unless otherwise specified.

No formal hypothesis testing was done for this study.

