## **9.6. Physical Examination**

The number and percentage of subjects with normal; abnormal, not clinically significant; or abnormal, clinically significant findings in the physical examination will be displayed at each study visit by body system and treatment group. Subjects having abnormal findings with description of Vitiligo are removed from table summary upon the sponsor request.

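### The early termination visit copies Week 24, the one late visit without a physical examination, so early-terminated subjects have no scheduled exit examination

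*Protocol*

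**What the plan says.** Protocol 5.5 applies to anyone who leaves before the final study visit. It defines the exit visit by one reference: "This visit should include the procedures and assessments that would be performed at the Week 24 visit". The final study visit itself is Week 25 (5.4), one week after Week 24.

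Protocol 5.1.3 leaves the timing of examinations wholly to the schedule: "Physical examinations will be performed according to the Schedule of Visits and Assessments". The schedule in 1.3 marks the examination at Screening, Baseline, Week 12 and Week 25, and SAP Table 1 marks the same four visits. Footnote a in both gives the scope: "Limited physical examination: skin, lungs, and heart only".

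The results are used in two ways. In the SAP, "findings in the physical examination will be displayed at each study visit by body system and treatment group" (9.6). In protocol 6.3.3, "Clinically significant changes observed during physical examination will be captured as adverse events and included in AE tabulations".

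SAP 3 says that no subject completed the treatment period and that "All the subjects that were currently enrolled have been early terminated".

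**The concern.** A subject who completes the study is examined at Week 25, as the last safety check on skin, lungs and heart. A subject who leaves early is sent through the Week 24 list, where that check does not appear. Neither document gives a reason for the difference. It looks like a side effect of pointing to Week 24 alone when the closing procedures are split between Weeks 24 and 25.

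In most trials this would affect a minority of subjects. Here 5.5 became the exit route for everyone enrolled. Two outputs are touched. The SAP 9.6 table has no scheduled exit examination to report. The AE tables also lose one route by which a clinically significant change would have been noticed.

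**Working it through.** No power, alpha or sample size figure is involved. The check is a reading of the two schedules, followed by simple counts.

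**Step 1. Which Week 25 procedures are missing from Week 24?** The rows come from protocol 1.3 and are the same in SAP Table 1.

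| Row marked at Week 25 | Also marked at Week 24? |
|---|---|
| Physical examination | No |
| Vital signs, height, weight | Yes |
| Regional BSA, regional VASI and FsIGA | Yes |
| Urine pregnancy test | Yes |
| Adverse event assessment | Yes |
| Concomitant medications | Yes |

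Six rows are marked at Week 25 and five of them at Week 24: 6 − 5 = 1. Copying Week 24 drops exactly one procedure, the physical examination.

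**Step 2. Is it restored elsewhere?** Section 5.1.3 refers back to the schedule. The fixed content of an unscheduled visit (5.6) is concomitant medications or procedures, AEs and the VASI scores, with no examination. Section 5.1 permits additional safety assessments at the Investigator's discretion. An exit examination is therefore possible but not scheduled.

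**Step 3. Scheduled examinations after Baseline, by time of exit.**

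| Subject | Scheduled post-baseline examinations | Of these, at exit |
|---|---|---|
| Completer | 2 (Day 85, Day 176) | 1 |
| Leaves after Week 12, before Week 25 | 1 (Day 85) | 0 |
| Leaves before Week 12 | 0 | 0 |

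**Step 4. Age of the last scheduled examination at exit.** In nominal days, ignoring visit windows, it is up to 85 − 1 = 84 days for a subject who leaves before Week 12. It is up to 169 − 85 = 84 days for one who leaves between Weeks 12 and 24.

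**Step 5. How many subjects have no scheduled post-baseline examination?** The documents do not give the share f who had the Week 12 visit. The share without is 1 − f. If f were 0.75, 0.5 or 0.25, it would be 25%, 50% or 75%; the full range is 0 to 100%. These values are illustrations only.

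**Step 6. What is kept at exit?** The Week 24 column includes AE assessment, vital signs, laboratory tests, ECG and the Investigator's local tolerability score. It also includes full-body BSA, T-VASI, FsIGA and photography.

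**Step 7. What follows the exit visit?** A completer has one further scheduled contact, at 176 − 169 = 7 days after Week 24. An early-terminated subject has none scheduled. The duty to collect SAEs for 30 days after the last application, or to the end of study if later (5.1.9, 5.7.2), applies to both, as does AE follow-up (5.7.5).

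**The case against.** The strongest reply is that little is lost. The examination is brief, the study drug is a topical cream, and the exit visit keeps the main safety measures. The Investigator still scores dermal response and other site effects there. All analyses are now descriptive (SAP 6), so no test or estimate depends on this table. This stands, and it is why the point is minor. It does not explain why completers are examined at the end and early leavers are not.

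Four stronger readings are tempting, and the documents do not support them.

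- *Subjects were abandoned after the exit visit.* No contact is scheduled, but the 30-day SAE duty and AE follow-up remain. Under 4.6 the Investigator must follow an AE that led to stopping product until it resolves or stabilises. Section 5.5 also sets no interval between last application and exit visit, so that visit may itself fall off treatment.
- *No exit examination took place.* The documents show only that none was scheduled. Discretionary examinations may have been done.
- *The SAP table conceals who was examined.* SAP 4.1 does say "The denominator for by-visit displays will be the number of subjects in the relevant study population with non-missing data at each visit". However, the three result categories in 9.6 are exhaustive, so within a body system and visit they sum to the number examined. SAP 7.1 reports the size of each population. A reader can largely see the shortfall at Week 12. Two limits remain. The rule in 9.6 that removes subjects with findings described as vitiligo disturbs that sum, at least for skin. Adding columns across visits also cannot give a count of distinct subjects.
- *Monitoring for viral reactivation and nail changes was lost.* Protocol 5.1 imposes it directly: "Subjects will be monitored for the reactivation of herpes simplex virus or varicella zoster virus following the initiation of phototherapy treatment". Nail monitoring for subjects treating the hands follows there, and changes go to the CRF. Neither is tied to the physical examination row.

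**Conclusion.** The gap is real and minor. Protocol 5.5 drops one procedure, the limited physical examination, from the exit of every early-terminated subject. Scheduled exit examinations number 0 for such subjects, against 1 for a completer. Scheduled examinations after Baseline number 0 or 1, depending on whether Week 12 was reached, against 2. By SAP 3 this applies to all enrolled subjects.

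The conclusion rests on reading the blank Week 24 cell as intended, which both schedules support, and on 5.5 meaning Week 24 without Week 25, which is what it says. How many subjects went unexamined after Baseline cannot be derived from the documents. The effect is confined to one descriptive safety table and one route into AE ascertainment.

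**What to change.** **Protocol 5.5, for any further use of this protocol:** define the early termination visit as the Week 24 procedures plus the limited physical examination scheduled at Week 25. The cost is a short three-system examination at a visit that already takes place.

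**SAP 9.6, for the terminated trial:** add, by treatment group and over the full Safety population, the number of subjects with any post-baseline physical examination. Add a footnote that 5.5 scheduled no exit examination. The cost is one or two table rows and a sentence. Examinations that were not done cannot be recovered, but their absence would be stated.

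**Optional:** one query per site asking whether a discretionary examination was done at exit, if the database is still open (the documents do not say). In a reused protocol, also name one telephone contact 30 days after the last application, so that the existing SAE duty has a scheduled means of collection. Neither is needed to close this point.

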## **5.6. Unscheduled Visit**

Unscheduled visits may be necessary to repeat testing following abnormal laboratory results, for follow-up of AEs, or for any other reason, as warranted in the judgement of the Investigator.

The following information will be collected for all subjects:

- Concomitant medications/procedures
- AEs
- F-VASI, F/N-VASI, FOREARM-VASI (forearms and elbows), HAND-VASI, and T-VASI

## **5.7. Adverse Events**

### **5.7.1. Adverse Event Definition**

An adverse event (AE) means any untoward medical occurrence associated with the use of a drug in humans, whether or not considered drug or device related. An AE can therefore be any unfavorable and unintended sign (including an abnormal laboratory finding), symptom, or disease temporally associated with the use of a medicinal (investigational) product or device, whether or not related to the medicinal (investigational) product or device.

The definition of an AE includes worsening of a pre-existing medical condition. Worsening indicates that the pre-existing medical condition has increased in severity, frequency, and/or duration or has an association with a worse outcome. A pre-existing condition that has not worsened during the study or involves an intervention, such as elective cosmetic surgery or a medical procedure while on study, is not considered an AE.

Adverse events resulting from device deficiency will also be reported. A device deficiency is inadequacy of a medical device related to its identity, quality, durability, reliability, safety or performance, such as malfunction, misuse or use error and inadequate labeling.

Irradiated site reactions will be considered adverse events if they exceed the expected irradiation reaction per the Investigator's discretion, require medical intervention (e.g. treatment with medication or dressings prescribed or applied by a physician) or discontinuation of phototherapy treatment.

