### **5.7.2. Serious Adverse Event**

The Investigator is responsible for ensuring that all serious adverse events observed by the clinical staff or reported by the subject that occur after signing of the informed consent through 30 days after the last day of the application of the investigational product or the end of study (whichever is later) are recorded in the subject's medical record and are submitted per SAE reporting requirements.

All SAEs will be reported to the Sponsor (or delegate) within 24 hours of becoming aware of the event, whether or not the serious events are deemed IP related. All serious event reporting will adhere to ICH E6: Guideline for Good Clinical Practice and ICH E2A: Clinical Safety Data Management: Definitions and Standards for Expedited Reporting.: The ERB/IRB will be notified of the Alert Reports as per HC, FDA, ICH and the IRB/ERB's policies and procedures. Refer to the Safety Reporting Instructions for SAE reporting.

An SAE is any AE that in the view of either the PI or Sponsor, results in any of the following outcomes: Death, a life threatening AE, inpatient hospitalization or prolongation of existing hospitalization, a persistent or significant incapacity or substantial disruption of the ability to conduct normal life functions, or a congenital anomaly/birth defect. Important medical events that may not result in death, be life threatening, or require hospitalization may be considered serious when, based upon appropriate medical judgment, they may jeopardize the subject and may require medical or surgical intervention to prevent one of the outcomes listed in the above definition. Examples of such medical events include allergic bronchospasm requiring intensive

treatment in an emergency room or at home, blood dyscrasias or convulsions that do not result in inpatient hospitalization, or the development of drug dependency or drug abuse.

Life threatening is defined as an AE that in the view of the PI or Sponsor, places the subject at immediate risk of death. It does not include an AE that, had it occurred in a more severe form, might have caused death.

Hospitalization does not include the following:

- Rehabilitation facilities, hospice facilities or respite care (e.g., caregiver relief)
- Nursing homes or skilled nursing facilities
- Emergency room visits
- Same day surgeries (as outpatient/same day/ambulatory procedures)
- <24 hour admissions for observation or evaluation

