Hospitalization or prolongation of hospitalization in the absence of a precipitating, clinical AE is not in itself an SAE. Examples include:

- Admission for treatment of a preexisting condition that did not worsen
- Hospitalizations for cosmetic elective surgery, social, and/or convenience admissions
- Pre-planned treatments or surgical procedures should be noted in the history documentation for the individual subject
- Diagnostic and therapeutic procedures, such as surgery, should not be reported as AEs; however, the medical condition for which the procedure was performed should be reported if it occurs during the reporting period and meets the definition of an AE. For example, an acute appendicitis that begins during the AE reporting period should be reported as an AE, and the resulting appendectomy should be recorded as treatment of the AE.

Unexpected is defined as an AE that is not listed in the IB or is not listed at the specificity or severity that has been observed; or is not consistent with the risk information described in the general investigational plan or elsewhere in the current study documentation.

If an SAE occurs to a subject on this study, contact the Medical Monitor within one business day of knowledge of event.

The definitions and reporting requirements of Health Canada/the Food and Drug Administration (FDA)/ICH Guidelines for Clinical Safety Data Management, Definitions and Standards for Expedited Reporting, Topic E2A will be adhered to. If any AEs are serious, as defined by ICH Guidelines for Clinical Safety, required procedures will be followed.

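### Protocol Section 5.7.1 both counts and excludes, as an adverse event, a pre-existing condition that worsens and is treated by a procedure on study

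*Protocol*

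**What the plan says.** The second paragraph of protocol Section 5.7.1 opens with an inclusive rule: "The definition of an AE includes worsening of a pre-existing medical condition". It then explains the term: "Worsening indicates that the pre-existing medical condition has increased in severity, frequency, and/or duration or has an association with a worse outcome". The next sentence is the exclusion. Its subject is "A pre-existing condition that has not worsened during the study or involves an intervention", and its remaining words give the examples and the consequence: "or involves an intervention, such as elective cosmetic surgery or a medical procedure while on study, is not considered an AE".

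Section 5.7.2 touches the same ground in three places:

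- It builds seriousness on the AE definition: "An SAE is any AE that in the view of either the PI or Sponsor, results in any of the following outcomes".
- Among hospitalizations that are not in themselves serious AEs, it lists "Admission for treatment of a preexisting condition that did not worsen".
- It says that procedures are not reported as AEs, but it adds this about their cause: "medical condition for which the procedure was performed should be reported if it occurs during the reporting period and meets the definition of an AE".

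The SAP (Sections 6.1.7 and 9.1) defines a treatment-emergent AE by its onset relative to the first application. It takes as given what an AE is and has no rule of its own for pre-existing conditions.

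This is current text. The protocol's summary of changes records only that Amendment 1 added worsening to the definition.

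**The concern.** Taken at its word, the excluding sentence has two grounds, and either is enough. The second ground, involvement of an intervention, is not limited to unworsened conditions, and its examples go beyond elective or pre-planned procedures. A worsened condition that led to a procedure is therefore caught by the exclusion, although the same paragraph has just said that worsening counts.

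What is at stake is whether the AE record is complete and whether sites build it in the same way. About 50 sites were planned (protocol Section 4.3), and two careful investigators could classify the same event differently. Following early termination, SAP Sections 8 and 10 limit efficacy reporting to descriptive F-VASI summaries. The safety tables therefore make up much of what the trial will report.

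**Working it through.** No arithmetic applies. The check sets the inclusive sentence (A) beside the excluding sentence (B) for each combination of worsening and intervention.

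- A: a pre-existing condition that has worsened is an AE.
- B: a pre-existing condition is not an AE if it has not worsened, or if it involves an intervention.

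| Worsened? | Intervention? | Under A | Under B | Result |
|---|---|---|---|---|
| No | No | not counted | excluded | agree: not an AE |
| No | Yes | not counted | excluded | agree: not an AE |
| Yes | No | AE | not excluded | agree: AE |
| Yes | Yes | AE | excluded | contradiction |

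Three of the four cases are consistent and one is not. The intervention limb of B also makes a difference only in the fourth case, because an unworsened condition is already excluded by the first limb. If the limb is confined to unworsened conditions, it adds no exclusion. If it is not confined, its only separate effect is to contradict A.

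The next question is whether other text resolves the fourth case.

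1. *Admissions, Section 5.7.2.* The carve-out covers only a condition that did not worsen. This is good evidence of intent, but it governs when a hospitalization is serious, not what an AE is.
2. *Procedure and condition, Section 5.7.2.* The two are separated, and the condition "should be reported if it occurs during the reporting period and meets the definition of an AE". That test leads back to Section 5.7.1, where the conflict lies. The worked example, acute appendicitis starting in the reporting period, is a new condition and not a worsened old one.
3. *Serious AEs, Section 5.7.2.* A serious AE must first be an AE, so an event dropped under B is dropped here too.
4. *SAP Sections 6.1.7 and 9.1.* Both start from AEs as recorded and inherit whichever reading the site used.

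Nothing in either document removes the contradiction.

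**The case against.** The strongest reply is that no sensible investigator would read the sentence this way. It follows directly on an unqualified rule that worsening counts, and its first example is elective cosmetic surgery. In context it can be taken to mean that merely having something done for a stable condition is not an AE. Section 5.7.2 supports that reading. So does nearby text in which intervention points towards counting an event: Section 5.7.1 makes irradiated-site reactions AEs when they need medical intervention, and Section 5.7.2 treats a possible need for intervention as a mark of an important medical event. The reference back to the AE definition is also not purely circular, since that definition includes the broad opening paragraph and the worsening sentence as well as the exclusion.

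There are partial safeguards. Protocol Section 6.3.3 captures clinically significant physical-examination changes as AEs. Serious-AE handling also relies on separate Safety Reporting Instructions, and the summary of changes mentions an eCRF completion guideline. Neither is available here, and either might give the intended rule.

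Most of this stands as evidence of intent, and it limits the likely practical effect. It does not make the paragraph consistent: the reader has to set aside the plain 'or' and infer the rule from a different section. Early termination reduces the value of a prospective rewording, but it leaves open how the events already recorded were classified.

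**Conclusion.** The contradiction is real and confined to one case: a pre-existing condition that worsens and is treated by a procedure on study. Applied literally, the excluding sentence leads to under-reporting of such events as AEs and hence as serious AEs. If sites read it differently, the classification is inconsistent. The documents do not show how any site read it, and the number of events affected cannot be derived from them. Correction is worthwhile because this is an operative safety definition and the remedy is small.

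A reader might infer more, and the documents do not support it:

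- *A loss concentrated at higher grades.* This would equate intervention in the severity scale of Section 5.7.5 with a procedure. Grade 2 there covers minimal, local or noninvasive measures, which need not be procedures, and the Grade 3 text does not use the term.
- *A general carry-through to the stopping rules in Section 5.9.* The limbs for ischemic or thromboembolic events and for severe infection are not worded in terms of AEs. That section also sends any condition possibly related to the product to the Medical Monitor.
- *Worsening cardiovascular disease or a growing skin lesion as the typical lost event.* A lesion that arises on study is not pre-existing. Exclusion criterion 19 bars prior melanoma anywhere, and prior basal cell carcinoma, squamous cell carcinoma or actinic keratosis in the treatable areas. For cardiovascular disease, the ischemic and thromboembolic stopping limb operates without reference to the AE definition.

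**What to change.** Reword the excluding sentence in Section 5.7.1 so that it agrees with Section 5.7.2, for example:

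> *A pre-existing condition is not an AE if it stays unworsened on study, including when an elective or pre-planned procedure is carried out for it. If it worsens, it is an AE whether or not it requires a procedure; the procedure is recorded as treatment and not as an AE.*

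If the eCRF completion guideline repeats the same wording, change it there too. The documents do not show whether it does.

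For the data already collected:

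- List the procedures recorded after the first application and set aside those noted as pre-planned in the subject's history, which Section 5.7.2 asks sites to document.
- For the rest, check whether the underlying condition worsened and has an AE record.
- State in the study report which reading was applied and how many records, if any, changed.

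This check can be only as complete as the recording of procedures. Section 5.6 names procedures at unscheduled visits, whereas the schedule in Section 1.3 lists only concomitant medications.

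The cost is one sentence, a single review of existing records and a line in the report. No new visits or data collection are needed.
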